#### **6.10 Agent Destruction/Disposal**

At the completion of the study, all unused study agent will be returned to NCI, DCP Repository according to the DCP “Guidelines for AGENT RETURNS” and using the DCP form “Return Drug List”.

The guidelines and the form are available on the DCP website.

## 7. CLINICAL EVALUATIONS AND PROCEDURES

### 7.1 Schedule of Events

Evaluation/ Procedure	Baseline Testing/Pre study Evaluation #	Randomization	Vacc #1	Vacc #2	Surgery	Post-Vacc Follow-Up Visit)	Final Follow-Up Visit
	Within 30 days prior to randomization		Day 0	Day 14 ±3 days	Day 28 ±5 days	1 month (30 days) ±7 days post-op	3-6 months post-op
Informed Consent	X						
Assess Eligibility	X						
Confirm Eligibility		X					
Registration	X						
Randomization		X					
Medical History	X						
Physical Exam	X						X
Vital Signs/ Height and Weight	X						X
Laboratory Tests	X				X 		
Cardiac evaluation 	X					X	
HLA blood draw for typing	X						
Immunological Samples			X		X 	X	X
Vital Signs Prior to Inoculation			X	X			
Agent Administration (Inoculation) 			X 	X 			
Pregnancy Test	X		X	X			
Research Tissue		X 			X		
Concomitant Medications	X		X	X	X 	X 	X
Adverse Events/Symptom Assessment			X	X	X 	X 	X
Local Reaction 			X 	X 			
Telephone Contact or Study Nurse Visit			X	X			

# Baseline testing may require multiple visits.

 Only limited ECHOs will be used as cardiac evaluation. No other tests are allowed. ECHO is to be done only in HLA-A2 positive participants (i.e., participants with confirmed DCIS will be HLA-typed prior to conducting ECHO). If ECHO has been done within 30 days prior to randomization and results showing a normal ejection fraction have been obtained prior to randomization, an additional ECHO is not needed at Baseline.

 Post inoculation vital signs will be assessed at 30 +/- 5 minutes post inoculation.

 Participants will be assessed for evidence of *in vivo* immunologic response by evaluation of the injection site 48-72 hours after each inoculation. Participants will either return to their study site or be contacted by phone for questioning regarding any systemic toxicity during the initial 48-72 hrs after inoculation. If they return to their study site, the local reaction at the inoculation sites will be examined and measured. For participants that do not return to their study site, a tool will be given, and instructions provided to measure the local reaction.

 An H&E stained slide and 10 unstained slides (or 11 unstained slides) from the initial breast biopsy should be sent to the laboratory of [name] at the address provided in **Section 10.3**. The biopsy slides should be sent within 6 weeks of randomization.

 May be assessed on the phone.

 May be performed up to 5 days prior to surgery relative to the visit target date.

 May be assessed the day prior to surgery in clinic or on the phone.

## 7.2 Baseline Testing/Prestudy Evaluation (Within 30 days prior to randomization)

Baseline Testing/Prestudy Evaluation interventions will be conducted within 30 days of randomization, may require multiple visits and will consist of the following procedures:

- Informed consent must be obtained prior to starting any further study procedures.
- Registration: Once informed consent has been signed, participants will be registered into the DMI database. The DMI database will assign a participant's PID upon completion of the registration process. Participants will also be registered into site-specific registry databases as applicable.
- Baseline medical history, to include a review of breast cancer history and previous medical history, previous surgery (*e.g.*, lumpectomy or mastectomy), chemotherapy and radiation therapy history, reproductive history, family history, demographic information, including age and race.
- Diagnosis of ductal carcinoma in situ by core needle biopsy; must be confirmed by review of the pathology report.
- Participants with confirmed DCIS will be HLA-typed. Because nelipepimut-S is an HLA-restricted peptide, the trial is limited to patients who are HLA-A2 positive (approximately 45% of the US population). HLA typing will be done locally by each site. Approximately 6-8 mL of blood will be drawn for HLA-typing (or as directed by the site HLA typing facility).
- Use of concomitant medications will be reviewed.
- A physical examination will be done that will include vital signs (temperature, blood pressure, heart rate, respiratory rate).
- Height, weight.
- Pre-study routine laboratory evaluations will include the following:
  - Platelets
  - Hemoglobin
  - Blood Urea Nitrogen
  - Alkaline Phosphatase
  - Lactate Dehydrogenase
  - Creatinine
  - Bilirubin
  - AST (SGOT)/ALT (SGPT)
- In women of child bearing potential a pregnancy test must be done within 30 days prior to Randomization. The pregnancy test will be repeated prior to each vaccination. Results must be known before vaccination. Either a serum or urine pregnancy test may be performed. If a urine pregnancy test is performed, the test must be done in the clinic.
  - If the pregnancy test result is positive at Baseline (any time before randomization), the participant is a Screen Failure.
  - If the pregnancy test result is positive prior to any Vaccination, do not vaccinate, take the participant off-study, complete the Off-Study Case Report Form (CRF), follow the pregnancy to term and complete the Outcome of Pregnancy Case Report Form (CRF).
- Cardiac evaluation: limited ECHOs to determine the ejection fraction. A normal ejection fraction, as defined by the participant's institution is required for randomization. Only limited ECHOs will be used as cardiac evaluation. No other tests are allowed. ECHO is to be done only in HLA-A2 positive participants (*i.e.*, participants with confirmed DCIS will be HLA-typed prior to conducting ECHO). If ECHO has been done within 30 days prior to

randomization and results showing a normal ejection fraction have been obtained prior to randomization, an additional ECHO is not needed at Baseline.

- Confirm eligibility: At the completion of the screening period eligibility must be confirmed. Only after eligibility is confirmed, can eligible participants be randomized.

### **Randomization**

- Once registration is complete, eligibility has been confirmed and eligibility CRF is entered into the web application, participants will be assigned a randomization number pre-generated by the database. Participants will be randomized to receive either NeuVax™ (nelipepimut-S; 1000 µg and 250 µg of GM-CSF) or GM-CSF alone. Participants will be blinded as to whether they are receiving nelipepimut-S/GM-CSF or GM-CSF alone.
- An H&E stained slide and 10 unstained slides (or 11 unstained slides) from the initial breast biopsy should be sent to [name] laboratory at the address provided in **Section 10.3**. The biopsy slides should be sent within 6 weeks of randomization.
- Randomization and Vaccination #1 may occur on the same day.

## **7.3 Evaluation During Study Intervention**

### **7.3.1 Vaccination #1 (Day 0 +/-3 days):**

#### ***Pre-Vaccination:***

- Pregnancy test prior to vaccination. Negative pregnancy result must be confirmed prior to vaccination:
  - If the pregnancy test result is positive prior to any Vaccination, do not vaccinate, take the participant off-study, complete the Off-Study Case Report Form (CRF), follow the pregnancy to term and complete the Outcome of Pregnancy Case Report Form (CRF).
- Blood for immunologic assays.
- One set of vital signs prior to inoculation.
- Adverse Events.
- Concomitant medications.
- Symptom assessment.

#### ***Vaccination***

- Agent administration: inoculation.
- Post inoculation vital signs will be assessed at 30 +/- 5 minutes after inoculation.

#### ***Post-Vaccination (48-72 hrs after inoculation):***

- Telephone contact with research nurse /or coordinator or nurse visit during the initial 48-72 hrs after inoculation: Participants will either return to their study site or be contacted by phone for questioning regarding any systemic toxicity during the initial 48-72 hrs after inoculation. If they return to their study site, the local reaction at the inoculation sites will be examined and measured. For participants who do not return to their study site, a tool will be given, and instructions provided to measure the local reaction. The NCI CTCAE version 4.03 graded toxicity scale will be utilized to assess local and systemic toxicity.
- Local reaction (for participants who return to the study site after inoculation):
  - Participants will be assessed for evidence of *in vivo* immunologic response by evaluation of the injection site 48-72 hours after each inoculation. The injection site reaction will be measured using the sensitive ball point pen method.
- Local reaction (for participants who do not return to the study site after inoculation):

- For participants that do not return to their study site, a self-assessment tool will be given, and instructions provided to measure the local reaction. This self-assessment tool is currently being utilized in the phase III trial evaluating NeuVax as well as two ongoing phase II trials evaluating NeuVax in combination with trastuzumab. The tool has been well received by the participants who appreciate its ease of use (the tool consists of a transparent piece of lightweight plastic with concentric circles depicted on it to allow for measurement) and the fact that it reduces the need to return to the study site for injection site assessment. To date, at MD Anderson, we have had 100% compliance with the use of the tool.

### **7.3.2 Vaccination #2 (Day 14 +/-3 days):**

- Pregnancy test prior to vaccination. Negative pregnancy result must be confirmed prior to vaccination:
  - If the pregnancy test result is positive prior to any Vaccination, do not vaccinate, take the participant off-study, complete the Off-Study Case Report Form (CRF), follow the pregnancy to term and complete the Outcome of Pregnancy Case Report Form (CRF).
- One set of vital signs prior to inoculation.
- Post inoculation vital signs will be assessed at 30 +/- 5 minutes after inoculation.
- Adverse Events.
- Concomitant medications.
- Symptom assessment.
- Local reaction (during the initial 48-72 hrs after inoculation).
- Telephone contact with research nurse /or coordinator or nurse visit during the initial 48-72 hrs after inoculation.

### **7.3.3 Day of Surgery (Day 28 +/-5 days):**

- Blood for immunologic assays will be drawn prior to the surgical procedure.
- Blood will be drawn for laboratory evaluations prior to surgery. Pre-surgery laboratory evaluations will include the following:
  - Platelets
  - Hemoglobin
  - Alkaline Phosphatase
  - Lactate Dehydrogenase
  - Bilirubin
  - AST (SGOT)/ALT (SGPT)
- Research tissue for tissue biomarkers (from the surgical specimen). For patients undergoing mastectomy, a representative sample of normal tissue maximally distant from the tumor will be obtained to assess for immune infiltrates.
- Adverse Events.
- Concomitant medications.
- Symptom assessment.

## **7.4 Evaluation at Completion of Study Intervention**

**7.4.1 Post Vaccinations Follow-Up Visit (Day +30 post op +/-7 days):** the post vaccinations follow-up visit will be conducted on Day +30 (+/- 7 days) post op and prior to initiating radiation, if post-op radiation is advised.

The following will be assessed:

- Adverse Events. May be assessed on the phone.
- Concomitant medications. May be assessed on the phone.
- Symptom assessment. May be assessed on the phone.
- Blood for immunologic assays.

Cardiac evaluation: limited ECHOs to determine the ejection fraction. Decreases of > 10% in the ejection fraction from baseline will be reported as an SAE and the participant experiencing the SAE will be managed according to the best clinical practice. Only limited ECHOs will be used as cardiac evaluation. No other tests are allowed.

## 7.5 Post-intervention Follow-up Period

**The Final Follow-Up Visit (3-6 Months post op):** the Final Follow-Up Visit will be conducted 3-6 Months post-surgery.

The following will be assessed:

- Physical exam.
- Vital signs.
- Adverse Events.
- Concomitant medications.
- Symptom assessment.
- Blood for immunologic assays.

## 7.6 Methods for Clinical Procedures

7.6.1 Local reaction assessment. The local reaction will be measured by either the research nurse /or coordinator (if the participant returns to clinic) or by the participant using the local reaction assessment tool, 48-72 hours after inoculation. The local reaction will be measured and reported in two dimensions.

## 8. CRITERIA FOR EVALUATION AND ENDPOINT DEFINITION

### 8.1 Primary Endpoint

#### **Primary Endpoint: Enumeration of nelipepimut-S-specific CTL**

The primary endpoint of the trial is to evaluate for nelipepimut-S-specific CTL response in vaccinated participants compared to participants receiving GM-CSF alone. The primary biomarker therefore is nelipepimut-S-specific CTL, which will be detected using a dextramer assay, which is a flow cytometry based assay. The number of nelipepimut-S-CTL will be determined in all participants, regardless of randomization to vaccine or GM-CSF alone, at the following time points: pre-vaccination, at the time of surgery (after two preoperative vaccinations), 1 month (+/- 7 days) after surgery, and 3-6 months at the time of the final study visit. The change in the number of nelipepimut-S-CTL for an individual participant between the pre-vaccination timepoint and the 1 month (+/- 7 days) after surgery timepoint will be used as the primary endpoint measure for this study. Planned subset analyses will be performed based on the extent of HER2 expression in the biopsy specimen (HER2 3+ vs HER2 0, 1+ or 2+), hormone receptor status, and menopausal status.

### 8.2 Secondary Endpoints

Secondary endpoints include:

8.2.1 Toxicity profile and frequency of adverse events in women with DCIS of the breast receiving nelipepimut-S vaccine as compared to women receiving GM-CSF alone.

- 8.2.2 Presence of DCIS at resection. The histologic data will be presented in tabular form to examine whether the vaccine treatment is associated with the absence of DCIS, induction of necrosis, reduction in histologic grade, or a reduction in the size of DCIS. These data will be descriptive only. The data will be obtained from the standard surgical pathology report generated as part of the patient’s clinical care. Formal comparisons of these parameters would likely require a larger sample size to see a statistically significant difference in presence of DCIS, induction of necrosis, or reduction in size of DCIS.
- 8.2.3 Difference in HER2 expression in the biopsy and the surgical specimen excised post-vaccination. HER2 scoring will be determined according to the American Society of Clinical Oncology/College of American Pathologists clinical guidelines [7]. Positive cases are those with circumferential membrane staining that is complete, intense, and within >10% of tumor cells (Score 3+). Negative cases are defined as those with no observable staining, or membrane staining that is incomplete and is faint/barely perceptible and within less than or equal to 10% of tumor cells (Score 0) or incomplete membrane staining that is faint/barely perceptible and within >10% of tumor cells (Score 1+). Equivocal or indeterminate cases are those with circumferential membrane staining that is incomplete and or weak/moderate and within >10% of tumor cells or complete and circumferential membrane staining that is intense and within less than or equal to 10% of tumor cells (Score 2+). Pre-vaccination and post-vaccination specimens will be compared.
- 8.2.4 Degree of lymphocyte infiltration. We will define intra-tumoral TIL as those within the basement membrane. Stromal TIL will be defined as those in the periductal/lobular stroma including the intralobular stromal infiltrate. Cells in the interlobular stromal inflammatory infiltrate will be excluded. All mononuclear cells will be scored but polymorphonuclear leukocytes will be excluded. Intra-tumoral and stromal TILs will be scored as a continuous variable and the percentage of in the surgical specimen will be compared to that in the pre-vaccination diagnostic biopsy.
- 8.2.5 We will utilize tissue-based cyclic immunofluorescence (t-CyCIF), a novel, highly multiplexed imaging modality that allows for the imaging of formalin-fixed, paraffin embedded (FFPE) tissue sections at subcellular resolution across 20-60 distinct antigen channels. Antibody panels that will be used include but may not be limited to an already optimized immune panel (Table 2).

Table 2. Optimized t-CyCIF immune panel.

Immune Panel:										
DAPI/Blue	Hoechst_1	Hoechst_2	Hoechst_3	Hoechst_4	Hoechst_5	Hoechst_6	Hoechst_7	Hoechst_8	Hoechst_9	Hoechst_10
FITC/Green	Background	Inos (Rab)	GrB	PD-L1	CD11b	CD4	IBA1	CD163	CD15	Arg1
Cy3/White	Background	pRB (Gt)	pSTAT1	FOXP3	CK7	Lag3	CD1cZ	CD11cZ	CD56	CD45RO
Cy5/Red	Background	BDCA2 (Ms)	CD45	PD1	MHCI	CD8	MHCII	CD20	CD14	SMA

Table: Optimized t-CyCIF immune panel

ImageJ an Matlab computer software will be used to analyze single cells and yield high-dimensional data analysis including tSNE analysis, dot plot analysis, heatmap analysis and scatter plots. The total number of prioritized immune cell types (Table 3) per mm^2 of tumor tissue and

the percent of specific types of immune cells of total cells will be assessed. Additionally, we will spatially resolve where cells are found and the proximity to other cell types.

Table 3. Prioritized human immune cell populations.

Prioritized Immune Cell Types	+/- PD-L1
Macrophages: CD45, CD11b, CD68	+
Macrophages: CD45, CD11b, CD68, CD163	+
M1 Macrophages: CD45, CD68, iNOS	+
M1 Macrophages: CD45, CD68, pSTAT1	+
M2 Macrophages: CD45, CD163, Arg1	+
Macrophages: CD45, CD68, PD-L1	+
MDSC - PMN: CD45, CD14(neg), CD15	+
MDSC-monocytic: CD45, CD14, CD15(neg)	+
Dendritic cells: CD45, IBA1(neg), CD11b	+
NK cells: CD45, CD56	-
T helper: CD45, CD4	-
Treg: CD45, CD3, CD4, FoxP3	-
CTL: CD45, CD3, CD8, GrB	-
T effector memory: CD45, CD3, CD8, CD45RO	-
T exhausted: CD45, CD3, PD-1	-
T activated: CD45, CD3, Ki67	-
B cells: CD45, CD20	-

8.2.6 Immune infiltrates in normal tissue maximally distant from the tumor (in mastectomy samples). In the mastectomy samples only we will perform core needle biopsies of the normal tissue, maximally distant from the tumor (*ex vivo* after the mastectomy if performed) and store for future studies of immune infiltrates.

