Data from our phase I/II trials evaluating the nelipepimut-S vaccine show a correlation between clinical efficacy and *in vitro* immune responses (specifically, enumeration of nelipepimut-S-specific CTL) [20] hence we will be looking at immunologic responses as the primary endpoint in this trial. The ability of the generated immune response to traffic to the tumor will be investigated as a secondary endpoint, specifically, we will be determining the degree of lymphocyte infiltration into the tumor in the resected surgical specimen. In order to determine the functional impact of the lymphocytes infiltrating the tumor, we will evaluate HER2 expression (*i.e.*, will evaluate HER2 expression in the pre-vaccination biopsy and the post-vaccination surgical specimen to determine if the antigen-specific immune response can eliminate the HER2+ clones in the tumor).

Completion of this study will determine the safety and immunologic efficacy of vaccination with NeuVax in patients with DCIS thereby providing necessary data to support the conduct of a larger study in DCIS as well as to build the foundation for a breast cancer prevention trial.

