#### 9.1.2 Histologic Responses

**Rationale.** Because this trial will administer vaccines before surgical therapy, the effects of immunization will be assessed on residual tumor at the time of surgical resection. A previous trial investigating a HER2-targeting dendritic cell vaccine in participants with DCIS showed a decrease in the number of HER2-expressing tumor cells in residual DCIS lesions suggesting that vaccination had stimulated an immune response capable of eliminating the HER2+ clones within the tumor. Dendritic cell vaccines are limited by their complexity which requires leukapheresis to obtain an individual participant's blood from which dendritic cells can be isolated, matured, and stimulated with the antigen of interest at a central processing facility. Our peptide vaccine strategy is also capable of stimulating an antigen-specific immune response but has the obvious advantage of being much simpler as it is an "off the shelf" therapy. In order to determine the intratumoral immune response stimulated in response to vaccination, we will evaluate for: 1) HER2 expression, and 2) the degree of lymphocyte infiltration (determined on H&E stained slides as well as determined by multiplex immunofluorescence), .

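### Section 8.2.3 reads HER2 only as the 0 to 3+ score with one 10% cut, so partial loss of HER2-expressing cells can leave the score unchanged; recording the percentage of cells at each intensity would fix this cheaply.

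*Combined protocol and SAP*

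**What the plan says.** Section 8.2.3 makes the difference in HER2 expression between the diagnostic biopsy and the surgical specimen a secondary endpoint. On the instrument it says: "HER2 scoring will be determined according to the American Society of Clinical Oncology/College of American Pathologists clinical guidelines". It then defines four levels:

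- For 3+: "Positive cases are those with circumferential membrane staining that is complete, intense, and within >10% of tumor cells (Score 3".
- The same intense, complete staining at or below the cut drops one level: "complete and circumferential membrane staining that is intense and within less than or equal to 10% of tumor cells (Score 2".
- Incomplete or weak/moderate circumferential staining above 10% is also 2+.
- Faint, incomplete staining is 1+ above 10% and 0 at or below it.

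The rule for change is one sentence: "Pre-vaccination and post-vaccination specimens will be compared".

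The purpose is given elsewhere. Section 2.3 says HER2 is read before and after vaccination "to determine if the antigen-specific immune response can eliminate the HER2+ clones in the tumor". Section 9.1.2 points to an earlier dendritic cell vaccine trial in DCIS that "showed a decrease in the number of HER2-expressing tumor cells in residual DCIS lesions".

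The next endpoint, in Section 8.2.4, is handled differently: "Intra-tumoral and stromal TILs will be scored as a continuous variable".

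No section names a percentage of positive cells, an H-score or any other graded HER2 measure. Sections 8.1 and 13.9 use HER2 only as categories. The multiplex panel listed in Section 8.2.5 has no HER2 channel, although the text leaves the panel open to additions. Section 13.5 plans between-arm comparison of within-person changes and lists tests for continuous and discrete markers, without saying which kind HER2 is.

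**The concern.** The purpose concerns how many tumor cells still express HER2. The instrument is a classification scale in which the share of stained cells counts only as above 10%, or at or below it. Within a category, the share can fall a long way without any change in the score. The only HER2 readout the plan defines could then show no difference for a woman whose lesion had lost a large part of its positive cells. In the other direction, a lesion close to 10% can change category after a small loss. With at most 48 women randomized, discarding within-category change is wasteful, because the reader must already judge the percentage against 10% to assign the score.

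**Working it through.** **No plan figure to reproduce.** The documents give no effect size, power or sample size for HER2. The only power figure, 82% in Section 13.1, is for the CTL change.

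**Inputs.** The 10% cut and the category definitions come from Section 8.2.3. The baseline percentage b of intensely, completely stained cells in a 3+ lesion is not in the documents, so a range is assumed. In both models below, cells that remain positive keep complete, intense staining.

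**Model A: cells lose HER2 but stay in the lesion.** With a fraction f lost, the remaining share is b(1 - f). The score stays 3+ while b(1 - f) > 10, that is, while f < 1 - 10/b.

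**Model B: positive cells are killed and leave the denominator.** The remaining share is b(1 - f) / [b(1 - f) + (100 - b)]. It stays above 10% while f < 1 - (100 - b)/(9b).

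| Assumed baseline b | Model A: score stays 3+ for losses below | Model B: score stays 3+ for losses below |
|---|---|---|
| 90% | 1 - 10/90 = 88.9% | 1 - 10/810 = 98.8% |
| 80% | 1 - 10/80 = 87.5% | 1 - 20/720 = 97.2% |
| 50% | 1 - 10/50 = 80.0% | 1 - 50/450 = 88.9% |
| 20% | 1 - 10/20 = 50.0% | 1 - 80/180 = 55.6% |
| 12% | 1 - 10/12 = 16.7% | 1 - 88/108 = 18.5% |

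More than half of the positive cells can be lost with the score still 3+ when b exceeds 20% (Model A) or 18.2% (Model B). Just above the cut, little is hidden.

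**What a percentage would show under Model A.**

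- 90% with half lost: 45% remains; score 3+ both times; change -45 points.
- 80% with three quarters lost: 20% remains; score 3+ both times; change -60 points.
- 90% with 85% lost: 13.5% remains; score 3+ both times; change -76.5 points.
- 60% with 85% lost: 9% remains; the score falls to 2+; change -51 points.

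The last line shows that the score does register some large losses.

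**What a percentage would show under Model B.** The percentage moves less, because killed cells also leave the denominator. At 90% with half killed, the share is 45/(45 + 10) = 81.8%, a change of about -8 points. At 80% with three quarters killed, it is 20/(20 + 20) = 50%, a change of -30 points. The score is 3+ throughout.

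**Other categories.** The 1+ category and the weak/moderate part of 2+ use the same cut with nothing graded above it. A fall from 80% to 12% weak/moderate staining, a relative loss of 1 - 12/80 = 85%, is 2+ both times.

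**Reach.** Section 13.9 hopes for roughly equal numbers at 0, 1+, 2+ and 3+. Applied to the 40 women evaluable for CTL, that is 40/4 = 10 at 3+, or about 27/4 = 6.75 on vaccine and 13/4 = 3.25 on control. About 30 would be in categories 1+ to 3+. Pairs with tissue at both times may be fewer.

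**The case against.** The guideline score is a standard choice for a secondary biomarker, and several points limit the concern.

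- **Elimination is visible.** Section 2.3 speaks of eliminating HER2-positive clones. Complete elimination would move a 3+ lesion to a lower score. A fall from intense to weak/moderate staining across the lesion would also change it. This stands: the gap concerns partial loss, which is the effect Section 9.1.2 describes from the earlier trial.
- **A graded measure is not excluded.** Section 13.5 allows for continuous markers, and the case report forms are not in the documents. A reader might infer that the plan commits to recording a fall from 90% to 15% as no change. It does not say so. What the text supports is that the category score is the only HER2 readout defined.
- **Not every woman is affected.** A reader might infer that a halving of positive cells is hidden in every 3+ woman above 20%. That holds only if the remaining cells keep complete, intense staining. How many women have high baseline percentages is unknown.
- **No decision rests on it.** The rule in Section 13.1 for calling the agent promising uses CTL effect size and adverse events. A reader might infer that the trial would wrongly conclude there was no immunoediting, but no HER2 success criterion or conclusion is laid down.
- **Numbers are small.** With about 10 women at 3+, no HER2 measure is likely to give a firm between-arm result in that group. For the histologic findings in Section 8.2.2, the protocol itself says formal comparison would likely need more participants.

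These points limit the consequence. They do not make the category score a good measure of change, because the same slides can yield a graded one.

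**Conclusion.** The point holds as a mismatch between purpose and measure in a secondary endpoint. Partial loss of HER2-expressing cells can leave the specified score unchanged. For a 3+ lesion the hidden relative loss runs up to 89% at an assumed baseline of 90%, 80% at 50% and 50% at 20%, and to under 17% at 12%. It is larger if positive cells are killed and leave the denominator. The figures rest on assumed baselines and on the remaining positive cells keeping complete, intense staining. The 1+ and weak/moderate 2+ categories have the same lack of gradation above 10%.

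The documents do not support a claim that the score misses all HER2 loss, or that the trial's main conclusion is at risk. The primary endpoint and the decision rule are untouched. This is an inexpensive improvement worth making before slides are read.

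**What to change.** In Section 8.2.3, have the reader record, for each biopsy and surgical slide, the percentage of tumor cells at each staining intensity, blind to arm and timepoint. Section 10.2 already blinds laboratories to participant information and visit; the text should also state blinding to arm for the HER2 reading.

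In Section 13.5, define the HER2 endpoint as the within-person change, surgical specimen minus biopsy, in the percentage of positive cells or in an H-score. Choose one in advance, and compare that change between arms with a named test. Keep the 0 to 3+ category as a descriptive table and for the subset analyses in Section 8.1.

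The cost is a few case report form fields and a sentence or two in each section, with no new tissue or stain. There are two drawbacks. Percentage estimates vary with the reading and with sampling, since a core biopsy is compared with an excision specimen. A percentage also understates cell killing when killed cells leave the denominator, as the Model B figures show. Even so, it registers a change where the category can register none.
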